3.5 Handling of Endpoints

[figure not shown]
3.5.1 IGA Response

Response (improvement) is defined as an IGA score, which is the primary endpoint, of 0 or 1 with improvement of at least 2 grades from baseline. Subjects without the above improvement will be handled as non-responders. In addition, subjects with missing IGA data will be handled as non-responders.

3.5.2 EASI Response (EASI 75, EASI 90, EASI 50)

Response (improvement) in EASI 75 is defined as a decrease by \geq 75% in the percent change from baseline in the total score of EASI. Subjects without the above improvement will be handled as non-responders. Response (improvement) in EASI 90 is defined as a decrease by \geq 90% in the percent change from baseline in the total score of EASI. Subjects without the above improvement will be handled as non-responders. Response (improvement) in EASI 50 is defined as a decrease by \geq 50% in the percent change from baseline in the total score of EASI. Subjects without the above improvement will be handled as non-responders. In addition, subjects with a missing total score of EASI will be handled as non-responders in EASI 75, EASI 90, and EASI 50.

4 Sample Size

5 Datasets for Analysis

5.1 Efficacy Analysis Set

Consists of all subjects who have received the IMP at least once.

5.2 Safety Analysis Set

Consists of all subjects who have received the IMP at least once.

5.3 Pharmacokinetic Analysis Set

Consists of all subjects who have received the IMP at least once and in whom a plasma drug concentration is determined for at least 1 time point after IMP administration.

5.4 Handling of Missing Data

Missing data are not imputed. For IGA response, EASI 75, EASI 90, and EASI 50, subjects with missing IGA or EASI scores are handled as non-responders.

6 Primary and Secondary Endpoints

6.1 Primary Endpoint (Primary Assessment Part)

• Success rate in IGA (percentage of subjects with an IGA score of 0 or 1 with improvement by at least 2 grades)

6.2 Secondary Endpoints

6.2.1 Efficacy Endpoint

- Response rate in EASI 90 (improvement of ≥90% in EASI), EASI 75 (improvement of ≥75% in EASI) and EASI 50 (improvement of ≥50% in EASI)
- Change from baseline in IGA score
- Percent change from baseline in the total score of EASI and each clinical sign score
- Change from baseline in the total score of POEM
- Change from baseline in the total affected BSA (%)

6.2.2 Safety Endpoints

- AEs
- Vital signs, body weight
- Clinical laboratory tests

6.2.3 Pharmacokinetic Endpoint

Plasma concentration of OPA-15406

7 Subject Disposition and Demographic and Other Baseline Characteristics

Unless otherwise noted, the summarizations described below will be performed for each of the following treatment groups and for all subjects: subjects receiving only the 0.3% formulation even at 4 weeks postdose and later (hereinafter referred to as the 0.3%)

formulation group) and subjects receiving the 1% formulation at least once at 4 weeks postdose or later (hereinafter, the 1% formulation [dose increase] group).

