3.1 Type/Design of Trial

This trial is a phase 3, multicenter, open-label, uncontrolled trial to evaluate the efficacy and safety of OPA-15406 ointment in infants younger than 2 years of age with atopic dermatitis.

1) Screening period

After obtaining informed consent from the subject's legal guardian, the investigator or subinvestigator will perform the screening examination. The screening period is defined as the period between the day of screening examination and the day of baseline examination (2 - 30 days).

2) IMP administration period

The IMP administration period is defined as the period between the day of baseline examination and the end of Week 52 examination (or the end of withdrawal examination). The primary assessment part is defined as the period between the baseline examination and the Week 4 examination, and the long-term extension part is defined as the period between the Week 4 examination and the Week 52 examination. Subjects who meet the inclusion and exclusion criteria at the baseline examination will be prescribed with the IMP. The IMP will be administered to the treatment area from the day of baseline examination twice daily for 52 weeks. If a subject discontinues the IMP administration between the day of baseline examination and the day of Week 52 examination, a withdrawal examination will be performed for that subject.

3) Trial period

The trial period for individual subjects is the period from the day of obtaining the written informed consent from the subject's legal guardian to the day of the Week 52 examination (or withdrawal examination). For subjects who missed the Week 52 examination (or withdrawal examination), the day of discontinuation will be the day when the investigator or subinvestigator determined that the subject was to be withdrawn from the trial. It does not include the follow-up period for AEs.

	Screening period (2 - 30 days)	IMP administration period (52 weeks)			IMF		
		OPA-15	assessment 0.3% 5406 ointm vice daily			[Long-term extension part] ^a 0.3% or 1% OPA-15406 ointment Twice daily	
Informed consent	Baseline examination	Week 1 examination	Week 2 examination	Week 4 examination	 •		Week 52 examination

a Long-term extension part (Week 4 - 52 examination)

- Subjects are scheduled to visit every 4 weeks, and the use of 1% formulation is also acceptable in accordance with dose increase criteria.

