3.2 Dosing Methods

3.2.1 Dose, Regimen, and Treatment Period

As the starting dose, 0.3% formulation will be administered twice daily (approximately 12 hours apart between morning and night administrations) for 52 weeks.

Primary Assessment Part (Baseline Through Week 4 Examination)

- The 0.3% formulation will be administered twice daily for 4 weeks.
- Even when the affected area is relieved, IMP administration should be continued there as the treatment area.

Long-term Extension Part (Week 4 Examination through Week 52 Examination)

- If subjects meet the dose increase criteria (see Section 3.2.2.1) at each 4-weekly assessment visit following the Week 4 examination, the 1% formulation will be used.
- When subjects show an improvement in skin symptoms and use of the 1% formulation is considered unnecessary, the dosage can be reduced to the 0.3% formulation. As a general rule, formulation switching should be done after the 4-weekly assessment (the formulation may be switched before the 4-weekly assessment if prompt dose reduction is required due to AEs or for other reasons).
- If all skin symptoms have resolved, IMP administration may be suspended based on the judgment of the physician. If skin symptoms relapse after interruption, IMP administration will be restarted.

The amount of IMP (g) per dose is 10 g/m² BSA, which is calculated as follows.

1) The subject's BSA (m²) will be calculated based on height and body weight at each examination, using the following equation.

BSA (m²) =
$$\sqrt{\frac{\text{Ht (cm)} \times \text{Wt (kg)}}{3600}}$$

BSA = body surface area; Ht = height; Wt = body weight

- 2) The treatment area will be specified.
- 3) The amount of IMP (g) per dose will be calculated as "subject's BSA (m²)" × "treatment area (%)" × "10 g/m²." Example: In case of a BSA of 0.7 m² and an affected BSA of 32%: 0.7 m² × 0.32 × 10 g/m² = 2.24 g

The method of IMP administration is specified in the separate procedure for IMP administration

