3.2.2 Dose Modification of the Investigational Medicinal Product

3.2.2.1 Dose Increase

For subjects receiving the 0.3% formulation with an IGA score of 2 or greater, the dose will be increased to the 1% formulation unless a concern about unacceptable tolerability is identified at a 4-weekly assessment (in the long-term extension part) including the Week 4 examination. Even for subjects with an IGA score of less than 2, the dose can be increased if judged necessary by the investigator or subinvestigator. Dose increase will be recorded together with the reason in the source documents and eCRF.

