7.1 Subject Disposition

The number of subjects for whom informed consent was obtained, the number of subjects receiving IMP administration, and the frequency distribution of completed or withdrawn subjects (the number and percentage of subjects, the same applies hereinafter) will be shown. The denominator of percentage is defined as subjects receiving IMP administration. For withdrawn subjects, the frequency distribution by withdrawal reason will be shown. The frequency distribution of subjects included in each analysis set will be shown.

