8.5 Exploratory or Other Analyses

9 Safety Analysis

In the safety analysis set, the following analyses will be performed. Unless otherwise noted, the summarizations described below will be performed for each of the following treatment groups and for all subjects: subjects receiving only the 0.3% formulation even at 4 weeks postdose and later (hereinafter referred to as the 0.3% formulation group) and subjects receiving the 1% formulation at least once at 4 weeks postdose or later (hereinafter, the 1% formulation [dose increase] group).

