9.2 Adverse Events

By using MedDRA (Ver 26.1), adverse events will be coded by system organ class (SOC) and preferred term (PT).

Regarding the following treatment-emergent AEs (TEAEs), the number and percentage of subjects with an onset will be calculated. If the same event occurred multiple times in the same subject, the most severe one will be used in analyses by severity, and the one with the earliest onset will be used in analyses by onset time. For skin and subcutaneous tissue disorders, analyses by the grade classification of the Common Terminology Criteria for Adverse Events (CTCAE) will also be performed.

- TEAE
- TEAEs by severity
- TEAEs with an outcome of death
- Serious TEAEs
- TEAEs leading to discontinuation of the IMP
- TEAEs leading to IMP treatment interruption
- TEAEs leading to IMP dose reduction
- TEAEs by CTCAE Grade (only for skin and subcutaneous tissue disorders)
- TEAEs at treatment areas
- TEAEs by onset time (\leq 4 weeks, >4 and \leq 12 weeks, >12 and \leq 24 weeks, >24 and \leq 36 weeks, >36 and \leq 52 weeks, and >52 weeks)

Adverse reactions (adverse events whose relationships with the IMP cannot be ruled out) will be analyzed in the same manner as TEAEs.

Serious TEAEs, TEAEs leading to discontinuation of the IMP, TEAE leading to IMP treatment interruption, and TEAEs leading to IMP dose reduction will be summarized by severity and CTCAE Grade.

For TEAEs that developed in \geq 5% of any treatment group and non-serious TEAEs that developed in \geq 5% of any treatment group, the number and percentage of subjects with an onset will be calculated.

In addition, TEAEs will be summarized in regard to the following items.

- TEAEs except for events that developed during the treatment interruption period
- TEAEs that developed by 4 weeks after IMP administration (only for all subjects)
- TEAEs that developed by 8 weeks after IMP administration
- TEAEs that developed in the treatment area
- TEAEs that developed in the treatment area by 4 weeks after IMP administration

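### The 0.3% and 1% groups are defined by treatment from Week 4 on but tabulated from Day 1, so by-group withdrawal, AE-discontinuation and non-responder rates are not comparable

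*Combined protocol and SAP*

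**What the plan says.** Section 7 sets the grouping for disposition and baseline summaries, and Section 9 repeats it for safety: "subjects receiving only the 0.3% formulation even at 4 weeks postdose and later (hereinafter referred to as the 0.3" group) on one side, and "subjects receiving the 1% formulation at least once at 4 weeks postdose or later" on the other, each shown beside all subjects. The opening of Section 8 uses the same split for efficacy.

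Before Week 4 there is one treatment. Section 3.2.1 states for the primary assessment part: "The 0.3% formulation will be administered twice daily for 4 weeks". Under Section 3.2.2.1 the 1% formulation first becomes available "at a 4-weekly assessment (in the long-term extension part) including the Week 4 examination".

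Stopping before Week 4 is foreseen. Section 3.1 reads: "If a subject discontinues the IMP administration between the day of baseline examination and the day of Week 52 examination, a withdrawal examination" follows. Sections 5.1 and 5.2 place anyone with a single dose in the efficacy and safety sets. No section says to which group an infant who stops before Week 4 belongs.

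The outputs under this split include completion and withdrawal (Section 7.1: "For withdrawn subjects, the frequency distribution by withdrawal reason will be shown"; tables CT-1 and CT-2) and, in Section 9.2, "TEAEs leading to discontinuation of the IMP" (tables CT-8.9.1.1 to CT-8.9.3.1). Section 8.2 reports IGA and EASI response by group, with missing scores counted as non-response (Sections 3.5 and 5.4). Section 9.2 restricts the general TEAE summary up to 4 weeks to all subjects. Disposition and discontinuation carry no such restriction.

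**The concern.** Membership of the 1% group is fixed by something that happens at Week 4 or later, while the counting of events starts at Day 1. An infant has to remain on treatment to be able to join the 1% group, so time before the first increase is free of withdrawal for that group by definition (immortal time). A reader who sees the two columns of CT-1, CT-2 or CT-8.9 side by side could take a lower 1% figure as better tolerability when part of it is produced by the definition.

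The same gap affects by-group response rates. From Week 8 on, an infant who stopped before Week 4 is a non-responder by rule. That failure falls either entirely on the 0.3% column or on neither column, depending on a reading that the SAP leaves open.

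**Working it through.** The documents give no figure to reproduce: no sample size text is available under Section 4, and no withdrawal rate or dose-increase share is stated. The check is therefore one of definitions, followed by arithmetic on assumed counts.

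**Definitions.** All infants are on 0.3% until the Week 4 examination, and 1% starts there at the earliest. An infant who stops before it can never be in the 1% group. There are two readings of the 0.3% group:

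- Natural reading: never received 1%. All early stoppers belong to it.
- Literal reading: on 0.3% at Week 4 and later. Early stoppers belong to no group, and the two columns do not add up to all subjects.

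**Assumptions (none from the documents).** N = 40 treated; e = 2 stop before Week 4; half of the remaining 38 increase, so n(0.3) = 19 and n(1) = 19; later withdrawal r = 10% in each group. The equal r is chosen to isolate the effect of the early stops.

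**Withdrawal.**

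- Natural reading, 0.3% group: (e + r × n(0.3)) / (n(0.3) + e) = (2 + 1.9) / 21 = 18.6%. The 1% group: 10.0%.
- Gap = e × (1 − r) / (n(0.3) + e) = 2 × 0.9 / 21 = 8.6 points, all of it from the definition.
- Literal reading: 10.0% against 10.0%, with columns totalling 38 of 40.
- All subjects, either reading: (2 + 3.8) / 40 = 14.5%.

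**Range of the gap on the natural reading**, with r = 10% throughout:

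| N | Early stops | Share increasing | n(0.3) | Gap |
|---|---|---|---|---|
| 60 | 1 | 30% | 41 | 0.9/42 = 2.1 points |
| 40 | 2 | 30% | 27 | 1.8/29 = 6.2 points |
| 40 | 2 | 50% | 19 | 1.8/21 = 8.6 points |
| 40 | 2 | 70% | 11 | 1.8/13 = 13.8 points |
| 30 | 6 | 70% | 7 | 5.4/13 = 41.5 points |

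The first and last rows are the extremes over N = 30 to 60, 1 to 6 early stops and 30% to 70% increasing. With e = 0 the gap is zero.

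**AE discontinuation** (N = 40; both early stops due to AEs; half of the rest increasing; none later). Natural reading: 2/21 = 9.5% (Clopper-Pearson 95% interval 1.2% to 30.4%) against 0/19. Literal reading: 0/19 against 0/19, so both events leave the by-group columns. All subjects: 2/40 = 5.0%.

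**Response from Week 8 on**, same counts, natural reading. The 0.3% rate cannot exceed 19/21 = 90.5%, while the 1% rate can reach 19/19.

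**After Week 4.** Increases are possible at any later 4-weekly visit. An infant who withdraws at Week 20 without an increase is a 0.3% withdrawal. One who increases at Week 24 had to stay until then. Starting the count at Week 4 therefore removes only part of the immortal time.

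**The case against.** The natural reading is the more plausible one. The word even in the definition suggests never moved to 1%, which is the complement of the 1% group and fits a disposition denominator of all treated infants. This stands, and it makes the literal branch the less likely of the two. It does not remove the problem, because on the natural reading all early stops fall on the 0.3% group.

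The trial is uncontrolled and plans no between-group test or difference. Dose increase is also triggered by an IGA of 2 or more, so the groups differ by selection in any case. This stands too. A reader might infer that the plan draws a false tolerability conclusion in favour of 1%, or that its group counts are wrong. The documents support neither: no such comparison is specified, and on the natural reading each count correctly describes its group.

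Much is reported in other ways: all-subjects columns, TEAEs by onset period (Section 9.2) and by concentration at onset (Section 9.2.2), and individual listings (CT-9.3, DREAS-1). This helps only in part. Section 9.2.2 states no denominator and does not name discontinuations, and nothing splits disposition by concentration. Only table titles are available, so columns and footnotes of CT-1, CT-2 and CT-8.9 cannot be checked.

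**Conclusion.** The definition needs correcting, but the reach is limited. By-group rates of withdrawal, AE discontinuation and non-responder-imputed response cannot be compared with each other as planned. The all-subjects results are unaffected, and so is the primary Week 4 analysis, which Section 8.1 specifies in all subjects.

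The 8.6-point gap and the 2.1 to 41.5 range rest entirely on assumed counts, and the upper end needs 6 early stops among 30 infants. The documents do not show that early stops will occur.

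Two stronger readings should be resisted. A reader might infer that early failures disappear from the non-responder analysis. That happens only in the by-group columns and only on the literal reading. A reader might also infer that counting from Week 4 makes the groups comparable. It does not, because later increases still require staying on treatment.

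**What to change.** 1. Define both groups among infants who receive IMP after the Week 4 examination. Put all other treated infants in a separate column, so that the three columns add up to all subjects. Use this in Sections 7, 8 and 9.
2. Report withdrawals and AE discontinuations between baseline and Week 4 for all subjects only, extending the restriction that Section 9.2 already applies to the general TEAE summary up to 4 weeks.
3. For withdrawals and AE discontinuations after Week 4, add a table by the concentration in use at stopping, over the treatment duration on that concentration. Section 9.1 already plans these durations, but the 0.3% time before the Week 4 examination must be taken out. Do not divide by the number of infants who ever used 1%: an infant increased, reduced again and then withdrawn would be a 0.3% event over a 1% denominator. State how a stop during an interruption is attributed.
4. Label the group columns as descriptive.

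The cost is a SAP definition, a third column that will be very small, and one extra table. No new data are needed.

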7.1 Subject Disposition

The number of subjects for whom informed consent was obtained, the number of subjects receiving IMP administration, and the frequency distribution of completed or withdrawn subjects (the number and percentage of subjects, the same applies hereinafter) will be shown. The denominator of percentage is defined as subjects receiving IMP administration. For withdrawn subjects, the frequency distribution by withdrawal reason will be shown. The frequency distribution of subjects included in each analysis set will be shown.

7.2 Demographic and Other Baseline Characteristics

In the efficacy analysis set, for age (month), sex, disease duration (month), body weight, height, body mass index (BMI), race, and AD severity, descriptive statistics or a frequency distribution will be shown depending on each characteristic. Descriptive statistics will be shown for age, disease duration, body weight, height, and BMI, and a frequency distribution will be shown for age group (<12 months, ≥12 months), sex, race, ethnicity, study country, and AD severity. By using MedDRA, medical histories/complication names will be coded by system organ class (SOC) and preferred term (PT). Medical histories/complication names will not be summarized but only listed.

In deriving the disease duration, the data will not be imputed when date data is missing. The year and month data will be used for calculation when the day is missing.

When "day, month, and year" are all available: (Administration start day, month, and year - AD onset day, month, and year + 1) / 30

When only "month and year" are available: (Administration start year \times 12 + Administration start month) - (AD onset year \times 12 + AD onset month) + 1

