3.3 Trial Population

Infants 3 months or older and younger than 2 years of age with AD and an IGA score of 2 or 3.

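### For infants whose onset day is missing, the disease-duration rule adds a whole month where the full-date rule adds one day, so it overstates duration by about one month

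*Combined protocol and SAP*

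**What the plan says.** SAP Section 7.2 lists "disease duration (month") among the baseline characteristics and gives two derivations.

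- **Full onset date available:** "Administration start day, month, and year - AD onset day, month, and year + 1) / 30". The result is elapsed days, counted inclusively, in 30-day months.
- **Onset day missing:** "The year and month data will be used for calculation when the day is missing". Year and month of each date are turned into a month count and subtracted, and 1 is added: "AD onset month) + 1".

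The section also states: "In deriving the disease duration, the data will not be imputed when date data is missing". It gives no reason for the different size of the added unit, no rounding rule and no upper limit on the result.

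On use, it says: "Descriptive statistics will be shown for age, disease duration, body weight, height, and BMI". Under Section 7 these summaries are given by treatment group and for all subjects. Section 3.3 defines the population: "Infants 3 months or older and younger than 2 years of age with AD".

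**The concern.** Both rules feed one variable and one row of the demographic table, so they should estimate the same quantity. They do not. In the full-date rule the +1 is a day, or 1/30 = 0.033 month. In the month-only rule it is a full month. A subject's recorded duration then depends on whether the onset day was captured as well as on the disease.

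In adults with years of disease, a month would hardly show. Here no subject has lived 24 months and the youngest are 3 months old. One month is a third of the longest possible duration in a 3-month-old, and about 17% (1/6) of a 6-month duration. Age is summarised in the same table, so a duration longer than life would be visible to a reader.

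**Working it through.** **Inputs.** The two formulas are from Section 7.2 and the age range of 3 to under 24 months is from Section 3.3. The plan states no figure to reproduce. The onset distribution and the share of missing onset days are not given, so anything that depends on them is an assumption.

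**Worked dates.** Full-date = (days + 1)/30; month-only = month difference + 1.

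| Onset to start | Full-date rule | Month-only rule |
|---|---|---|
| 15 Mar to 15 Jun 2022 | 93/30 = 3.10 | 3 + 1 = 4 |
| 28 Feb to 1 Jun 2022 | 94/30 = 3.13 | 4 + 1 = 5 |
| 31 May to 1 Jun 2022 | 2/30 = 0.07 | 1 + 1 = 2 |
| 15 Jun 2021 to 15 Jun 2022 | 366/30 = 12.2 | 12 + 1 = 13 |
| 1 Jun to 30 Jun 2022 | 30/30 = 1.0 | 0 + 1 = 1 |

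**Average size.** Both rules were applied to every start date in a two-year span, with onset 0 to 730 days earlier. True duration is elapsed days/30.4375, where 30.4375 = 365.25/12.

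- Month-only minus true: mean +1.01 months.
- Month-only minus full-date: mean +0.80 month, range -0.40 to +2.00. Month-only is the larger in 97% of date pairs.
- By time since onset, the mean gap between the rules falls from 0.95 month (onset within 3 months) to 0.65 month (near 2 years). Mixes of durations from 30-180 days to 180-730 days give means between about 0.7 and 0.9.

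The gap between the rules is below 1.0 because the 30-day divisor inflates the full-date result: 30.4375/30 = 1.015, or about 1.5%. The full-date rule therefore exceeds true duration by 1.01 - 0.80 = 0.21 month on average over this span.

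**Is the added month a correction for the unknown day?** No. Without it, the month difference misses true duration by only 1.01 - 1 = +0.01 month on average. The unknown day makes the month difference noisy but does not bias it.

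**Duration against age.** Take an infant born 20 January with onset in January (day unknown) and treatment starting 25 April. The month-only rule gives 4 - 1 + 1 = 4 months. The infant has lived 95 days, and 95/30.4375 = 3.1 months.

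A simulation assumed ages of 92 to 729 days and onset uniform between birth and start. Month-only duration exceeded completed months of age in 100% of cases with onset in the birth month, about 48% with onset in the next calendar month, and about 10% overall. Against exact age, the overall figures are about 10% for the month-only rule and 1.9% for the full-date rule.

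**Effect on the table.** If a share p of subjects has no onset day, the reported mean is higher than under the full-date rule by about 0.8p month. That is 0.08 month at p = 10%, 0.40 at p = 50% and 0.80 at p = 100%. These shares are illustrations only.

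**The case against.** **Inclusive counting.** Both rules add one unit at their own resolution, and Section 3.4 likewise counts the start day as Day 1. Without the +1, an onset in the start month gives 0 months. This explains how the formula may have arisen, but it does not reconcile the rules. Counting the start day adds a day, which the full-date rule already does; it does not add a month.

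**The full-date rule is not exact either.** A 12-month-old with onset at birth gets 12.2 months, so exceeding age is not unique to the month-only rule. The rules also agree for some date pairs and reverse slightly for others. All of this is true, but the month-only excess is much larger and nearly always in one direction.

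**How far the consequence reaches.** A reader might infer that impossible durations will appear in the tables and listings. The documents do not support that. The rule applies only when the onset day is missing, and neither the share of such subjects nor the onset distribution is given. No listing title in Appendix 3 names derived disease duration. If nearly all onset dates have the same precision, the table is almost consistent within itself, although durations derived wholly from month-only dates would still be about a month too long.

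A reader might also infer that efficacy conclusions are affected. They are not. Disease duration is absent from the primary analysis (Section 8.1) and from the subgroup list (Section 8.4), and the trial is open-label and uncontrolled.

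**Conclusion.** The month-only rule is wrong as written. For each subject with a missing onset day, it overstates true duration by about 1.0 month on average and exceeds the full-date rule by about 0.8 month on average. The overstatement against true duration follows from the formulas alone. The size of the gap between the rules also depends on the durations assumed. That a duration can exceed age is shown by a direct example; how often it would do so rests on the uniform-onset assumption and the unknown share of missing days.

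The importance is minor. One descriptive baseline variable is affected, and no inference depends on it. The correction is still worth making because the error is relatively largest in the youngest infants and is easy to remove.

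**What to change.** Make two changes in Section 7.2, together:

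1. Remove the +1 from the month-only formula.
2. Divide by 30.4375 instead of 30 in the full-date formula.

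Removing the +1 alone leaves a mean gap of 0.80 - 1 = -0.20 month, caused by the divisor. With both changes, month-only is +0.01 month from true duration and full-date is +0.03 (its one inclusive day), so the mean gap is about -0.02 month. Single date pairs can still differ by up to about a month either way, because the day is unknown: 31 May to 1 June gives 1 against 2/30.4375 = 0.07.

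One small downside is that onset in the start month then gives 0 months; the SAP should say that this is accepted.

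A cap at the subject's age is not needed. If one is wanted, apply it only against exact age computed from the date of birth on the same scale. Section 7.2 does not say how age in months is derived. A cap at completed months would cut correct values, such as 3.9 months in an infant recorded as 3 months old.

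The cost is a short SAP edit and the matching change to one derivation in the programs. No new data are needed.
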